#### 6.4.3 Primary endpoint reporting

For primary endpoint analysis, paired Wilcoxon tests will be performed on adjusted WID scores associated with disease risk, cellular ageing, or exposure, in cervical samples at baseline and month 6 of the intervention (adjusted for immune cell composition). For visualisation, points and lines may be coloured by compliance score, delta BMI, or smoking status at the end of the intervention. Data will be visualised using Spaghetti plots and may additionally be visualised using violin/box plots with overlayed jitter plots.

Analyses will be presented separately per sub-study and a comparison between the two randomised arms in the diet intervention study may be conducted. The analysis is predominantly conducted ITT, but separate subgroup analyses may be conducted as follows:

- $\bullet$  per protocol, if at least 30 individuals have a cumulative compliance score of more than 80%
- diet intervention: timing of fasting, breakfast versus dinner cancellation

Mixed-effects models could provide a complimentary method of reporting individual effects over time.

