## 3.6 Sample size

The sample size of n = 60 per group is based on an initial estimation of the potential clinically relevant effect and variance as part of the preceding FORECEE project: a total of 60 participants are required to detect a difference of 0.2 in DNA methylation indices (e.g. WID-BC index), assuming a standard deviation of 0.44, at a statistical power of 0.94 and a significance level of 0.05. There are no preliminary data for longitudinal changes in the WID scores, thereby TirolGESUND acts as a pilot study to define effect sizes and variance for larger prospective studies in the future.

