#### 4.1.2 Exclusion criteria

- 1. Relevant underlying conditions
  - (a) Current or previous malignant tumour or cancer
  - (b) Current or previous significant cardiovascular disorder Women with elevated blood pressure are allowed to participate as long as it is well controlled under their current medication
  - (c) Current or previous metabolic disorder (e.g., diabetes type I or II) In the dietary intervention arm, participants with current hypothyroidism/Morbus Hashimoto will be excluded as the switch to intermittent fasting may require a adjustment of their medication
  - (d) Current or previous psychiatric disorder (e.g., eating disorder, depression)
- 2. Current pregnancy or lactation period
- 3. Total hysterectomy
- 4. Known current or previous premalignant lesion of the cervix uteri (CIN2/3)
- 5. Concurrent participation in another interventional trial

Participants for which inclusion criteria 1b, c, d, 2, 3, and 5 occur after inclusion in the study will be excluded from the study.

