# 5.2 Analysis populations

The primary analysis will be an intention to treat (ITT) analysis in all participants, separately per study arm. A per protocol (PP) population will be all study subjects completing the study period with a median compliance above or equal to 80% (if sufficient n, e.g. n=30) or alternatively stratifying group by compliance above and beyond the compliance median. Additionally, the effect of compliance to the intervention will be evaluated using linear mixed-effects models with the compliance score as covariate. Timing may be coded as days since baseline rather than categorical variable (M2, M4, M6).

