#### General study characteristics

• dropout rate

Is the dropout rate consistent with the literature (approximately 15-20% for lifestyle

interventions)? The analysis will be reported separately for the two sub-studies and randomised trial arms.

- *compliance* What is the compliance across the two sub-studies?
- sign-up rate

Out of participants that originally registered interest, how many wanted to finally participate and how many were included after meeting the criteria?

Moreover, the study will describe longitudinal alterations in a variety of health parameters (see also Fig. 2):

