#### 6.4.4 Secondary endpoint reporting

To investigate the magnitude and temporal dynamics of changes in methylation indices for each surrogate tissue, namely cervical, buccal, and blood, linear mixed-effects models will be estimated, combining tissues where applicable. The use of random slopes and intercepts will be explored (R package lme4 or nlme, lmer function). Compliance score, sample cell composition, BMI, smoking status, or other factors identified during exploratory data analysis may be used as covariates. Additionally, in a descriptive manner, the change from baseline will be reported within each tissue and paired comparisons will be carried out. Examples of linear models (covariates may be altered or extended) are provided below:

$$model_{intermittent \ fasting} = lmer(score \sim compliance + sample \ type + BMI + ic + age_{baseline} + (time|id), data = data)$$
(1)

$$model_{smoking \ cessation} = glmer(score \sim compliance + sample \ type + smoking \ status + ic + age_{baseline} + (time|id), data = data)$$
(2)

Separate models per sample type may be even more informative, this will be explored during exploratory data analysis.

Using models based on equations in equations 1 and 2, the data will be characterised as follows:

- 1. Estimation of average changes in all participants
- 2. Estimation of changes for individual participants
- 3. Characterisation of degree of heterogeneity across participants (variance across participants, quantified by random effects)
- 4. Identify factors (fixed effects) that predict changes (e.g. compliance score)

Beta estimation will be conducted using maximum likelihood estimation. Following model fitting, residuals will be visualised and qq plots will be generated. If p values are needed for reporting, these will be obtained via Kenward-Roger estimation in the R package lmerTest. A sensitivity analysis will be conducted using either complete case analysis or multiple imputed values

Comparison between sample types may be done via incorporation of data into mixed effects models with an additional covariate (sample type). The sample type with the biggest changes in association with the compliance score may be the most suitable surrogate type for monitoring longitudinal health effects.

Data will be visualised using spaghetti plots, colouring by compliance score and applying facet wraps by sample type.

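### The primary analysis is labelled ITT in all participants, but its paired baseline–month 6 test can use only women with both cervical samples, and no required analysis covers the others

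*SAP*

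**What the plan says.** Section 5.2 sets the population: "The primary analysis will be an intention to treat (ITT) analysis in all participants, separately per study arm".

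Section 6.4.3 sets the test: "paired Wilcoxon tests will be performed on adjusted WID scores associated with disease risk, cellular ageing, or exposure, in cervical samples", taken "at baseline and month 6 of the intervention (adjusted for immune cell composition"). It gives no rule for a woman without a month 6 sample, or for one whose sample fails the quality control of section 6.4.1.

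Mixed models appear in several places with differing status. They are optional for the primary objective (sections 2.2.1 and 5.4.1) and complementary in section 6.4.3. They are firmly planned for longitudinal dynamics in section 6 and for the secondary epigenetic endpoints in section 6.4.4. The summary table in section 6.16 also seems to list one among the primary rows, but the table is broken in the text available.

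The only missing-data step is in the secondary section 6.4.4: "A sensitivity analysis will be conducted using either complete case analysis or multiple imputed values".

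Section 4.1.2 adds: "Participants for which inclusion criteria 1b, c, d, 2, 3, and 5 occur after inclusion in the study will be excluded from the study". The numbering matches the exclusion list, so the reference to inclusion criteria looks like a slip.

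Sections 3.11 and 5.3 say that data are collected whether or not a woman complies, and that non-compliers are kept.

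**The concern.** The population label and the test cannot both hold. A woman without a usable month 6 cervical sample contributes nothing to the paired test, whatever she gave at baseline, month 2 or month 4.

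The study has no control group, so no comparator can reveal or offset selective loss. If women with a poorer response are more likely to be missing at month 6, the observed change is shifted toward benefit. The same women are missing for every score, so several scores can be shifted together, and the success rule in section 5.4.1 asks for a significant reduction in two or more. The SAP recognises such selection for the optional follow-ups at months 12 and 18 (section 5.4.3), but has no corresponding step for month 6.

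**Working it through.** **Inputs**
- Group size: "The sample size of n = 60 per group is based on an initial estimation" (section 3.6). The same section gives a difference of 0.2, SD 0.44, power 0.94 and significance level 0.05.
- Dropout: "approximately 15-20% for lifestyle" interventions (section 5.4.2), given as a literature benchmark.
- Assumed here: two-sided test, and 0.44 is the SD of the change. Section 3.6 states neither.

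**1. Reproducing the stated power.** For a paired comparison, power ≈ Φ(δ/SD × √n − 1.96).
- n = 60: 0.2/0.44 × √60 − 1.96 = 3.52 − 1.96 = 1.56, so power = 0.941. The noncentral t gives 0.934.
- The stated 0.94 is reproduced with 60 complete pairs, so it makes no allowance for dropout.

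**2. Complete pairs after dropout**

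| Dropout | Women lost of 60 | Pairs | Power (normal) | Power (t) | Enrolment needed for 60 pairs |
|---|---|---|---|---|---|
| 15% | 9 | 51 | 0.90 | 0.89 | 60/0.85 = 70.6, so 71 |
| 20% | 12 | 48 | 0.88 | 0.87 | 60/0.80 = 75 |

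The diet sub-study pooled (120 women) keeps 102 to 96 pairs and power above 0.99. Samples failing quality control would break further pairs; the SAP gives no rate for this.

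**3. Size of a possible bias.** Assume that completers change by -0.20 and women who leave change by 0. The change in all women is -0.20 × (1 − dropout).
- 15%: -0.20 × 0.85 = -0.17. The completers' figure is 0.20/0.17 = 1.18 times as large.
- 20%: -0.20 × 0.80 = -0.16. The ratio is 0.20/0.16 = 1.25.

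**4. False reductions when the true mean change is zero.** Simulation: 20,000 runs, n = 60, normal changes with SD 0.44, paired t test, women with less favourable change more likely to be missing. The correlation r between change and dropout propensity is assumed. The table gives the chance of a significant reduction for one score (nominal 0.025).

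| Dropout | r = 0 | r = 0.2 | r = 0.3 | r = 0.5 |
|---|---|---|---|---|
| 15% | 0.025 | 0.056 | 0.088 | 0.171 |
| 20% | 0.024 | 0.069 | 0.110 | 0.240 |

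With r = 0 there is no inflation.

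**5. Whether the mixed models already fill the gap.** They do not, as written. The ITT mixed model in section 5.4.1 is optional and would carry the compliance score, which is measured after baseline. Example models (1) and (2) in section 6.4.4 contain time only in the random part. Without a fixed time effect they do not estimate the mean change at month 6.

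**The case against.** The strongest reply is that the study is exploratory and a pilot, that non-adherent women are followed and kept, that mixed models over all visits are planned, and that attrition will be visible through the dropout report, the flowchart and CONSORT reporting. Much of this stands, and it rules out several stronger readings that a reader might infer:

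- *The test is restricted to compliers.* It is not. Under sections 3.11 and 5.3, a woman who fails to quit or fast stays in if she gives a month 6 sample.
- *Month 2 and month 4 data are unused.* This is true of the Wilcoxon test only. Sections 6 and 6.4.4 use them in mixed models. The criticism concerns the status and specification of those models.
- *Section 4.1.2 removes women's data from the ITT set.* It says that the women are excluded from the study and is silent on data already collected. It is ambiguous, and no direct contradiction is shown.
- *The trial itself expects 15-20% dropout.* The figure is a literature benchmark against which observed dropout will be compared.
- *The result is biased toward benefit by 18-25%.* This follows only if women who leave have exactly zero change. The SAP has no figures on selective dropout at month 6.

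The exploratory aim lowers the stakes but does not make the population label right. Reporting how many women left also does not show what the result would be with them included.

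**Conclusion.** The point holds in a limited form and should be fixed. The analysis called ITT in all participants is a complete-pairs analysis, and no required analysis of the primary endpoint includes women without a usable month 6 sample. This follows from the text alone.

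The size is conditional. At the cited literature dropout, 9 to 12 of 60 women per group leave the test and power falls from 0.94 to about 0.87-0.90, which is modest. Bias is the larger worry, but its existence, direction and size depend on dropout being related to response. Under the zero-change scenario the overstatement is 0.03 to 0.04 on a change of 0.20; under unrelated dropout it is nil.

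**What to change.** 1. In sections 5.2 and 6.4.3, label the paired Wilcoxon test a complete-pairs analysis.
2. Make a mixed model over baseline and months 2, 4 and 6 a required ITT analysis of the primary endpoint. It should have visit as a fixed factor and no compliance term, and include every woman with a baseline sample. Its cell-composition adjustment must be reconciled with section 6.4.2, which bases the correction on baseline values.
3. Add a sensitivity analysis that sets women without a usable month 6 sample, including quality control failures, to no change from baseline.
4. State in section 4.1.2 that data already collected from women excluded after inclusion stay in the ITT set, and correct the reference to inclusion criteria. No position is taken here on whether these women stop the intervention.

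The cost is SAP wording and a little more analysis; the visits are already planned. The mixed model assumes data missing at random, and women with only a baseline sample add little to it on change. It therefore does not by itself cure dropout related to unseen change, which is why item 3 is needed.

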#### 6.4.4 Secondary endpoint reporting

To investigate the magnitude and temporal dynamics of changes in methylation indices for each surrogate tissue, namely cervical, buccal, and blood, linear mixed-effects models will be estimated, combining tissues where applicable. The use of random slopes and intercepts will be explored (R package lme4 or nlme, lmer function). Compliance score, sample cell composition, BMI, smoking status, or other factors identified during exploratory data analysis may be used as covariates. Additionally, in a descriptive manner, the change from baseline will be reported within each tissue and paired comparisons will be carried out. Examples of linear models (covariates may be altered or extended) are provided below:

$$model_{intermittent \ fasting} = lmer(score \sim compliance + sample \ type + BMI + ic + age_{baseline} + (time|id), data = data)$$
(1)

$$model_{smoking \ cessation} = glmer(score \sim compliance + sample \ type + smoking \ status + ic + age_{baseline} + (time|id), data = data)$$
(2)

Separate models per sample type may be even more informative, this will be explored during exploratory data analysis.

Using models based on equations in equations 1 and 2, the data will be characterised as follows:

- 1. Estimation of average changes in all participants
- 2. Estimation of changes for individual participants
- 3. Characterisation of degree of heterogeneity across participants (variance across participants, quantified by random effects)
- 4. Identify factors (fixed effects) that predict changes (e.g. compliance score)

Beta estimation will be conducted using maximum likelihood estimation. Following model fitting, residuals will be visualised and qq plots will be generated. If p values are needed for reporting, these will be obtained via Kenward-Roger estimation in the R package lmerTest. A sensitivity analysis will be conducted using either complete case analysis or multiple imputed values

Comparison between sample types may be done via incorporation of data into mixed effects models with an additional covariate (sample type). The sample type with the biggest changes in association with the compliance score may be the most suitable surrogate type for monitoring longitudinal health effects.

Data will be visualised using spaghetti plots, colouring by compliance score and applying facet wraps by sample type.

The abovementioned aspects cover the dynamics of epigenetic indices. Additionally, it will be investigated whether epigenetic indices in certain tissues are associated with other clinical or molecular health-related biomarkers via correlation analysis. No causality can be established for these factors.

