# 3.4 Quantification of compliance

Participants will be semi-continuously monitored for adherence to the intervention using the following measures:

- Smoking cessation:
  - Reported cigarettes smoked in the last 7 days via personal coaches
  - Urine cotinine levels at month 2, 4, and 6
- Intermittent fasting:
  - Reported compliance with the intermittent fasting regime over the last 7 days via coaches
  - Capillary  $\beta$ -hydroxybutyrate levels throughout the intervention as measured three times a week using FORA6 blood monitoring at home available only for a subset of participants

Adherence to the compliance will also be reported by study doctors at each visit (compliance higher or lower than 75%).

A compliance score will be derived, taking into account the days compliant and the days between the visitations. If a subject reported compliant on all days between two visitations, the compliance score is 100%. Compliance will be cross-checked for concordance

using objective measurements (urine cotinine levels for smoking cessation, and capillary  $\beta$ -hydroxybutyrate levels for the diet intervention). High compliance with smoking cessation should result in no measurable cotinine levels in urine, although the metabolite is only short-lived. High compliance with diet intervention should result in elevated ketone body measurements in capillary blood. As an additional quantitative score of compliance, it may also be measured in number of cigarettes since last visit and cumulative ketone body measures in capillary blood.

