# 6 Analysis

Analyses will be conducted and reported separately per sub-study (i.e. smoking cessation and intermittent fasting) after all samples for the month 6 timepoint have been collected. Key analyses will be performed on the ITT population. A per-protocol analysis will be conducted if sufficient individuals are available with above 80% compliance (n=30), or alternatively and additionally a subgroup analyses split by median compliance score (above and beyond, respectively). Descriptive statistics of dynamics over 6 months without an intervention will be reported and if sufficient individuals are present per study arm (n  $\geq 10$ ) that did not adhere, these may be used as a nested control group; although this number is small, it could be informative for dynamic changes without intervention.

The longitudinal manner of data collection enables baseline-controlled pairwise comparison (paired t or Wilcoxon test) for each participant at baseline and after 6 months; linear mixed effects-models may also be employed. Longitudinal dynamics and repeated measurements per participant, evaluating data from baseline, 2, 4, and 6 months, will be assessed using linear (or non-linear) mixed-effects models to account for inter-individual heterogeneity and differences in response (random intercept and slopes, if appropriate). In the intermittent fasting group, cross-sectional analyses may be used to compare effects for use with and without ketogenic supplement. Change from baseline may be reported in a descriptive manner.

Methylation data will be adjusted for sample cell type composition which is known to influence methylation levels. Many of the assessed factors are influenced by age. Dependence on other, non-intervention related covariates will be investigated during the exploratory data visualisation and assessment, and factors may be associated as covariates in mixed-effects models if necessary.

If a number of participants does not adhere to the intervention but continues to provide samples and the assumption of common support holds, we may be able to explore the average treatment effect (ATE) and causal average treatment effect (CATE) using causal inference (g methods) via covariate adjustment for selected secondary outcomes (in particular longitudinal DNA methylation analyses).

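### Models (1) and (2) enter compliance at an unstated level, with no baseline value and no fixed time or compliance-by-time term, so they cannot show that compliance predicts change

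*SAP*

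**What the plan says.** Section 3.4 builds the score from visit intervals: "A compliance score will be derived, taking into account the days compliant and the days between the visitations". It fixes the top of the scale in the same way: "If a subject reported compliant on all days between two visitations, the compliance score is 100" per cent. No section gives a value for the baseline visit.

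Two other sections use a score per woman. The per-protocol population in section 5.2 is "all study subjects completing the study period with a median compliance above or equal to 80" per cent. Section 6.4.3 allows an analysis "per protocol, if at least 30 individuals have a cumulative compliance score of more than 80" per cent.

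Compliance is meant to enter mixed models. Section 5.2 is firm: "the effect of compliance to the intervention will be evaluated using linear mixed-effects models with the compliance score as covariate". Section 6.4.4 is permissive: "Compliance score, sample cell composition, BMI, smoking status, or other factors identified during exploratory data analysis may be used as covariates". Section 6 puts baseline in the longitudinal models, "evaluating data from baseline, 2, 4, and 6 months, will be assessed using linear (or non-linear) mixed-effects models".

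Models (1) and (2) in section 6.4.4 contain compliance, sample type, BMI or smoking status, immune cell composition and baseline age as fixed main effects, plus (time|id). They have no fixed time term and no product of compliance with time. They are offered as examples whose covariates may change. Their listed uses include average change and the fixed effects that predict change. The section adds: "The sample type with the biggest changes in association with the compliance score may be the most suitable surrogate type".

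**The concern.** A covariate predicts change in a longitudinal model through its interaction with time, or through a time-varying exposure with time itself also modelled. The written models do neither, and the compliance variable is not pinned down. The analyst must choose between an interval score and a participant score, and with an interval score must invent a baseline value. These choices lead to different models that answer different questions.

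The study has no control group, so common drift over six months is the main rival explanation for any change. A model that credits drift to compliance would make the intervention look responsible. The surrogate-tissue choice has the same exposure: it could pick the tissue that drifts most rather than the one that follows adherence.

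**Working it through.** **1. The plan's own figure.** Section 3.6 gives n = 60, difference 0.2, SD 0.44, alpha 0.05 and power 0.94. Taken as a paired comparison, two-sided (sidedness is not stated): 0.2/0.44 × √60 = 3.521; 3.521 − 1.960 = 1.561; Φ(1.561) = 0.941. It reproduces. The point below does not depend on it, but borrows 0.2 as the drift and 0.44 as the scale of variability.

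**2. Interval score, baseline left missing.** Four visits × 60 women = 240 rows per tissue, of which 60 (25%) are baseline. Over three tissues this is 180 of 720. For the 120 women in the diet sub-study it is 120 of 480 per tissue. No dropout is assumed. A complete-case fit loses all of these rows.

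The cost in precision, if a linear time term is present (the written models lack one): take a random-intercept model with residual SD 0.311, so that a month 0–6 difference has SD 0.311 × √2 = 0.44. The SE of the common slope is 0.311/√(60 × Σ(t − mean)²).
- Months 0, 2, 4, 6: sum of squares 20, SE 0.0090.
- Months 2, 4, 6: sum of squares 8, SE 0.0142.

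For a change of −0.2 over six months (0.0333 per month in size), power is Φ(0.0333/0.0090 − 1.96) = 0.96 with baseline and Φ(0.0333/0.0142 − 1.96) = 0.65 without.

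**3. Interval score, baseline coded 0.** The score then rises from 0 to its usual level at month 2 for everyone. Its correlation with a plain before/after flag is 0.65, 0.93 or 0.99 for compliance uniform on 0–1, 0.5–1 or 0.8–1.

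Simulation A: 60 women, common change −0.2 unrelated to compliance, interval compliance Beta(6, 1.5), between-woman SD 0.40, residual SD 0.311. Without fixed time, compliance is significant in about 77% of runs with a random intercept and about 68% with random slopes. With fixed time added and baseline still 0, the rate is about 5%.

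**4. Participant-level score, main effect only.** With a random intercept, the coefficient reflects each woman's average over the four visits. On a 0–1 time scale the visits average (0 + 1/3 + 2/3 + 1)/4 = 0.5, so a true effect of −0.40 on the six-month change appears as −0.40 × 0.5 = −0.20.

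**5. All codings side by side.** Simulation B: 4,000 runs, 60 women, compliance uniform on 0.5–1.0, between-woman SD 0.35, residual SD 0.27, common drift −0.2, fits with known variances. In each pair, the first figure is for a fitted slope SD of 0 and the second for 0.2. The true effect is −0.40 on the six-month change per full unit of participant-level compliance.

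| Compliance term tested | Significant, no true effect | Mean coefficient, true −0.40 | Significant, true −0.40 |
|---|---|---|---|
| Interval, baseline 0, no time | 89% / 75% | −0.18 / −0.16 | 93% / 82% |
| Interval, baseline 0, fixed time | 5% / 5% | −0.03 / −0.02 | 7% / 5% |
| Interval, baseline dropped | 5% / 5% | −0.12 / −0.10 | 9% / 7% |
| Participant, main effect | 5% / 5% | −0.20 / −0.14 | 9% / 6% |
| Participant × time, with fixed time | 4.5% / 3% | −0.38 / −0.38 | 22% / 16% |

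The 93% and 82% in the first row are not useful power: nearly the same coefficient arises from drift alone (−0.165 and −0.147). Only the last row holds the error rate and comes close to the true effect.

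**The case against.** A reader might infer that the score exists only between visits, so that the models must either lose baseline or turn compliance into a before/after flag. The SAP does not support that. Sections 5.2 and 6.4.3 use a median or cumulative score per woman, which can be attached to every row. Section 6.4.4 does not say that its covariate varies by visit, and nothing in the plan sets baseline to 0 or drops it.

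A reader might also blame the false positives on zero coding. They come from the absent fixed time term, as step 3 shows. Zero coding with time modelled is safe on that count, although in simulation B it then recovers almost none of the true effect.

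Nor does this undermine the primary result: the paired Wilcoxon test of section 6.4.3 does not use compliance.

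The defence can add that the equations are examples, that compliance is optional in section 6.4.4, that section 5.2 considers coding time in days, and that the study is described as mainly exploratory. All of this is fair and limits the reach. It does not remove the point. Section 5.2 commits to evaluating compliance in this way, section 5.4.1 allows the same covariate in an ITT mixed model for the primary objective, and freedom to alter covariates supplies neither a level, nor a baseline value, nor an interaction. The sensitivity analysis by complete cases or multiple imputation does not define compliance at baseline either.

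**Conclusion.** The point holds in this form: the level and baseline value of compliance are not stated, and under none of the readings examined do the written main-effect models deliver the stated aim of finding factors that predict change. The size depends on the reading: 25% of rows lost; about 68–77% false positives (75–89% under the second set of assumptions) if baseline is 0 and time is not fitted; or a true effect reduced to half or less if the score is per participant.

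The row counts assume no dropout. The rates and coefficients rest on variances, a compliance distribution and a drift of −0.2 that the SAP does not give for this purpose, so they show direction and rough scale rather than a forecast. The correct model is not powerful either: 22% or 16% for an effect of −0.40 per full unit of compliance in simulation B. The reach is the secondary epigenetic models, the surrogate-tissue comparison and the optional mixed model of section 5.4.1.

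**What to change.** In section 6.4.4:

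- Define one compliance score per participant, choosing between the median of section 5.2 and the cumulative score of section 6.4.3, and attach it to all her rows, baseline included. State that no baseline row is dropped for want of a compliance value.
- Add a fixed time effect and a compliance-by-time interaction to models (1) and (2), keeping (time|id).
- Base the statement on factors that predict change on that interaction. Base the surrogate-tissue comparison on the same interaction by tissue, through separate models or a further product with sample type, with confidence intervals.
- Apply the same specification if the mixed model of section 5.4.1 is used.

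The cost is a few lines of SAP text and one derived variable, with no new data. The downside is that a participant-level score ignores visit-to-visit variation in adherence. If that variation matters, cumulative compliant days since baseline, which is truly 0 at baseline, can be fitted alongside fixed time as a supplementary analysis. Given the low power, the interaction is best reported as an estimate with its interval, and a non-significant result should not be read as no dose-response.
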